### **6.1.3. Subjects to Analyze**

Three analysis populations will be defined:

- The Safety population will include all subjects who are enrolled and received at least one confirmed dose of investigational product. This population will be used for all safety analyses and will be defined separately for each treatment arm.
- The Intent-to-Treat (ITT) will include all subjects randomized in the study. This population will be the primary analysis for the analysis of efficacy endpoints.

- The PK population will include all subjects who are randomized and receive at least one application of investigational product and have at least one analyzed PK sample.

#### **6.1.4. Background and Demographic Characteristics**

Demographics, baseline disease characteristics, baseline height, weight, and BSA will be summarized descriptively for all enrolled subjects.

#### **6.1.5. Study Disposition**

The number of subjects randomized, receiving IP, completing study, and withdrawing prematurely (with reason for withdrawal) will be summarized by treatment group.

#### **6.1.6. Investigational Product Application Compliance**

The number of subjects with important protocol deviations and/or eligibility deviations will be summarized by category and by treatment group.

### **6.2. Efficacy Evaluation**

Efficacy endpoints were evaluated by an independent rater as described in [Section 5.2.1](#).

#### **6.2.1. Primary Efficacy Endpoint**

The primary efficacy endpoint will be the proportion of subjects achieving F-VASI75 ( $\geq 75\%$  improvement from baseline in Facial Vitiligo Area Scoring Index (F-VASI) score) at Week 24.

The primary endpoint of ‘Proportion of subjects achieving F-VASI75 ( $\geq 75\%$  improvement from baseline in Facial Vitiligo Area Scoring Index (F-VASI) score) at Week 24 will be analyzed using a Cochran-Mantel-Haenszel test stratified by the stratification factors study site and Fitzpatrick Skin Type (I-III vs. IV-VI). The analysis will be performed on the Intention-to-Treat (ITT) population and missing data will be imputed using multiple imputation.

#### **6.2.2. Secondary Efficacy Endpoints**

Continuous secondary endpoints will be analyzed using Analysis of Covariance with treatment and stratification factor as independent variables. Binary secondary endpoints will be analyzed similarly to the primary endpoint.

The secondary efficacy endpoints will include:

- Proportion of subjects achieving F-VASI75 ( $\geq 75\%$  improvement from baseline in F-VASI score) at visits prior to Week 24.
- Percent change from baseline in F-VASI score at all visits.
- Percent change from baseline in facial body surface area (F-BSA) at all visits.
- Proportion of subjects achieving F-VASI50 ( $\geq 50\%$  improvement from baseline in F-VASI score) at all visits.

- Proportion of subjects achieving F-VASI90 ( $\geq 90\%$  improvement from baseline in F-VASI score) at all visits.
- Proportion of subjects in each category of VNS at specified visits.
- Change from Baseline in the VNS at specified visits.
- Change from Baseline in the VitiQoL at specified visits.
- Patient Global Impression of Change-Vitiligo (PaGIC-V), proportion of patients in each PaGIC-V category at specified visits.
- Proportion of subjects who report PaGIC-V of very much improved or much improved during the treatment period.
- Time to achieve F-VASI50.
- Time to achieve F-VASI75.
- Time to achieve FsIGA of clear or almost clear (0 or 1).
- FsIGA of clear or almost clear (0 or 1).
- FsIGA of clear or almost clear (0 or 1) plus 2-grade improvement from baseline.
- Time to achieve a PaGIC-V of very much improved or much improved.

The binary secondary endpoints will be analyzed using a Cochran-Mantel-Haenszel test stratified by study site, age  $\leq 30$  or  $> 30$  years, and Fitzpatrick Skin Type (I-III vs. IV-VI).

#### **6.2.3. Exploratory Endpoints**

- Percent change from baseline in combined face and neck body surface area (F/N-BSA) at all visits.
- Percent change from baseline in surface area BSA (hands/forearms/elbows) at all visits.
- Percent change from baseline in BSA affected across all treatable sites (face, neck, hands, forearms, elbows) at all visits.
- Proportion of subjects achieving F/N-VASI50 ( $\geq 50\%$  improvement from baseline in F/N-VASI score) at all visits.
- Proportion of subjects achieving F/N-VASI75 ( $\geq 75\%$  improvement from baseline in F/N-VASI score) at all visits.
- Proportion of subjects achieving F/N-VASI90 ( $\geq 90\%$  improvement from baseline in F/N-VASI score) at all visits.
- Percent change from baseline in FOREARM-VASI (forearms/elbows) score at all visits.
- Percent change from baseline in HAND-VASI (hands only) score at all visits.

- Serum levels of ARQ-252.
- The proportions of subjects who maintain 80% treatment compliance with both application of ARQ-252 cream 0.3% or vehicle cream and phototherapy or sham phototherapy up through 24 weeks.

### **6.3. Safety Evaluation**

Descriptive statistics will be calculated for safety data and presented by visit and treatment group for quantitative safety data and frequency counts will be compiled for classification of qualitative safety data. Summaries of local tolerability will be presented by visit and treatment group.

#### **6.3.1. Adverse Events**

All AEs occurring during the study will be recorded and classified on the basis of MedDRA terminology for the safety population. AEs will be summarized by treatment group, the number of subjects reporting AEs, system organ class, preferred term, severity, relationship, and seriousness.

Serious adverse events (SAEs) will be listed by subject. SAEs will be summarized by treatment group, severity, and relationship to study treatment. For AEs, each subject will be counted only once within a system organ class or a preferred term using the event with the greatest relationship and greatest severity.

All information pertaining to AEs noted during the study will be listed by subject, detailing the verbatim description given by the Investigator, preferred term, system organ class, start date, stop date, severity, action taken regarding IP, corrective treatment, outcome, and IP and/or phototherapy relatedness. The event onset will also be shown relative (in number of days) to date of first application.

In addition, a listing of subjects who prematurely discontinue from the IP due to adverse events will also be provided.

#### **6.3.2. Local Tolerance Assessment**

For the Investigator's and Subject's assessment, the numeric application site reaction scores will be summarized individually by using number and percentage of subjects by visit, as well as mean/median scores.

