***Footnotes from table above:***

- j Tolerability assessments should be recorded prior to study drug application for Investigator assessment and 10-15 minutes post-drug application for subject ('0-3' burning/stinging assessment). Investigators will specify if any application site reaction is due, in whole or in part, to the effects of phototherapy treatment. Only the Investigator assessment will take place on Week 24.
- k Digital Photography will be conducted at all sites for all subjects. Required study photos will be taken of the treatment areas during the Baseline Visit. In addition, a photo of the facial target patch will be taken as reference for the VNS assessment. Fixed, multi-angle photos will be taken at select sites for additional evaluation.
- l A urine pregnancy test will be administered to all females of child-bearing potential. A negative result is required for continued participation in the study, and results must be available prior to dispensing of study drug at each visit.
- m Serum pregnancy testing will be performed at Screening; a negative result is required for participation in the study.
- n FSH will be performed (if indicated) at Screening to confirm post-menopausal status.
- o PK samples will be collected from all subjects at Baseline, Week 4, Week 12, and Week 24. The samples will be drawn prior to application of the investigation product in the clinic. Subjects should apply investigational product 11-12 hours before the PK collection time.
- p NB-UVB Phototherapy treatment will occur in the clinic at the Baseline Visit prior to the initial IP application. The treatment will be per the NB-UVB Treatment Protocol ([Appendix 1](#)) and be tailored per the subject's Fitzpatrick Score. The subject will be provided with the phototherapy unit in addition to a USB stick which will be inserted into the unit to obtain phototherapy data during the course of the treatment period.
- q Subjects should be instructed return the USB stick from the phototherapy unit to site for the uploading of the phototherapy data. Once the data has been uploaded by the site staff, a new USB stick should be provided to the subject to insert into the NB-UVB phototherapy unit.
- r IP kits will be dispensed based on % BSA affected. See IP Handling Manual for details.
- s Subjects to apply assigned IP in clinic at these visits. The time of application will be documented.

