## **5.9. Treatment Stopping Rules**

If a subject has non-cutaneous adverse events of concern, clinically significant laboratory values or any condition that the Investigator determines could possibly be related to the investigational product, the Investigator should immediately contact the Medical Monitor to discuss if the subject should be discontinued from treatment with investigational product.

Treatment for any individual subject should be interrupted if the Investigator observes the following:

- If a subject develops an application site reaction with the clinical appearance of an ‘irritation reaction’, and with a severity of a Dermal Response Score of 5 (erythema, edema, and papules) on Local Tolerability Assessment ([Section 5.1.8](#)), treatment should be interrupted for up to one week and may then be resumed if the reaction has, in the opinion of the Investigator, adequately resolved.

For application site reactions treatment should be discontinued:

- If the application site reaction reoccurs, treatment should be discontinued permanently, and the subject followed until the reaction resolves.

Treatment for any individual subject will be discontinued if the subject experiences:

- A serious adverse event (SAE) or a clinically significant non-serious AE which in the opinion of the Principal Investigator or Medical Monitor warrants discontinuation from the study for that subject's well-being.
- A treatment-emergent severe (Grade 3) laboratory abnormality (confirmed by repeat sample) which in the opinion of the Principal Investigator or Medical Monitor warrants discontinuation from the study for that subject's well-being.
- A severe infection (Grade 3 or higher)
- An ischemic or thromboembolic cardiovascular event (regardless of Grade)
- A severe adverse event within the system-organ class of Cardiac Disorders (Grade 3 or higher)

As noted above, study treatment must be discontinued immediately in the event of a female subject's pregnancy.

In the event of a medical emergency where unblinding is required to provide medical care to the subject, refer to the most current IRT plan and Breaking Treatment Codes ([Section 4.4.1](#)). Contact the Medical Monitor and the Sponsor promptly.

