## 4. Statistical Analysis and Reporting

### 4.1. Introduction

Data processing, tabulation of descriptive statistics, calculation of inferential statistics, and graphical representations will primarily use SAS (release 9.4 or higher). If the use of other software is warranted, the final statistical methodology report will detail what software was used for what purposes.

Continuous (quantitative) variable summaries will include the number of subjects (n) with non-missing values, mean, standard deviation (SD), median, Q1, Q3, minimum, and maximum.

Categorical (qualitative) variable summaries will include the frequency and percentage of subjects who are in the particular category or each possible value. In general, the denominator for the percentage calculation will be based upon the total number of subjects in the study population for the treatment group, unless otherwise specified. The denominator for by-visit displays will be the number of subjects in the relevant study population with non-missing data at each visit.

The minimum and maximum will be reported with the same degree of precision (i.e., the same number of decimal places) as the observed data. Measures of location (mean, median, Q1, and Q3) will be reported to 1 degree of precision more than the observed data and measures of spread (SD) will be reported to 2 degrees of precision more than the observed data.

Percentages will be presented to 1 decimal place, unless otherwise specified.

No formal hypothesis testing was done for this study.

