## **9.2. Local Tolerability Assessments**

The investigator's assessment of the application site reaction will be summarized by study visit and treatment group using both categorical methods (number and percentage of subject with each score) as well as continuous methods (e.g., mean, median, etc.). Categorical summaries will be provided for dermal response as well as other effects. No inferential statistical tests will be performed. This assessment should be performed prior to the application of IP in the study site. Subjects not meeting this condition on baseline visit are completely removed from the table summary.

The subject's assessment of the application site reaction will be summarized similarly. This assessment should be performed 10 – 15 minutes after the application of IP in the study site. Subjects not meeting this condition on baseline visit are completely removed from the table summary.

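### Local tolerability is summarised only visit by visit, so no output gives the share of subjects in each arm who ever reached a given score

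*Protocol*

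**What the plan says.** Protocol 6.3 states: "Summaries of local tolerability will be presented by visit and treatment group". Protocol 6.3.2 adds that, for both the Investigator's and the subject's assessment, "the numeric application site reaction scores will be summarized individually by using number and percentage of subjects by visit", with mean and median scores. SAP 9.2 has the Investigator scores "summarized by study visit and treatment group using both categorical methods" and continuous ones, and treats the subject scores in the same way. SAP 4.1 fixes the denominator: "The denominator for by-visit displays will be the number of subjects in the relevant study population with non-missing data at each visit".

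Three scales are involved (Protocol 5.1.8):
- **Dermal Response**, 0 to 7, and **Other Effects**, A to G: scored by the Investigator before application.
- **Burning/stinging**, 0 to 3: scored by the subject 10 to 15 minutes after application in the clinic.

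Footnote j of the schedule in Protocol 1.3 says: "Only the Investigator assessment will take place on Week 24".

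On stopping, Protocol 5.9 says that after an irritation reaction with a Dermal Response Score of 5, "treatment should be interrupted for up to one week and may then be resumed" if the reaction has adequately resolved. It then says: "If the application site reaction reoccurs, treatment should be discontinued permanently, and the subject followed until the reaction resolves".

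**The concern.** Each row of a by-visit table is a point prevalence among those assessed that day. The usual question about a topical product combined with light is different: what proportion of subjects in each arm had, at any time, a reaction of a given grade? The planned rows do not answer it. They cannot be added, because one subject may be counted at several visits. No single row is the answer either, unless every affected subject is affected at that visit.

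The denominator also changes for reasons tied to the outcome. A subject taken off the cream has no in-clinic application and so gives no burning/stinging score. A subject who exits early has Week 24 procedures (Protocol 5.5), which include the Investigator scores but not the subject score. Later rows therefore lean towards those who tolerated treatment.

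At stake is whether the report can state, by arm, how many subjects reached each grade on the only systematic scales specific to the application site.

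**Working it through.** The plan states no reaction rate, timing or cumulative figure, so there is none to reproduce. The check has two parts.

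**1. Do other outputs supply the per-subject count?**
- *AE tables.* Protocol 6.3.1 counts each subject once per preferred term or system organ class, at greatest severity. SAP 9.1 gives the number and percent of subjects with TEAEs by maximum severity, and of those stopping study drug or phototherapy because of a TEAE. Protocol 4.6 treats events under Section 5.9 as adverse events. A reaction that ends treatment is therefore counted per subject.
- *What they leave out.* Protocol 5.7.1 makes an irradiated-site reaction an AE only if it exceeds the expected reaction in the Investigator's judgement, needs medical intervention or stops phototherapy. Nothing requires every scored reaction to be reported as an AE. AEs carry CTCAE grades (Protocol 5.7.5), so no AE table shows who reached, say, Dermal Response 3. The SAP 9.1 discontinuation counts cover any TEAE, not local reactions separately.

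**2. How far can the ever-affected share lie from the visit rows?**

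Inputs from the documents: *K* = 6 assessments on each scale. The Investigator has Weeks 4, 8, 12, 16, 20 and 24. The subject has Day 1 and Weeks 4 to 20. A main arm has 150 subjects, and dropout is 15% (Protocol 6.1.2). Rates and timing are assumptions. The ratio below is the ever-affected share divided by the highest visit percentage.

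*Constant risk h per visit, one reaction then removal:* ever = 1 − (1 − h)^6, and each row shows h.

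| h | Ever affected | Ratio |
|---|---|---|
| 1% | 5.85% | 5.85 |
| 2% | 11.42% | 5.71 |
| 5% | 26.49% | 5.30 |

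Adding other dropout of 15% over six visits (per-visit loss 1 − 0.85^(1/6)) lowers these ratios to 5.48, 5.35 and 4.98.

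*Timing varied, 9 of 150 ever affected (6%), each removed after one reaction (expected counts):*

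| Pattern | Highest row | Ratio |
|---|---|---|
| Even, 1.5 per visit | 1.5/142.5 = 1.05% | 5.7 |
| Half at Week 4, then halving | 4.5/150 = 3.0% | 2.0 |
| Two-thirds at Week 4 | 6/150 = 4.0% | 1.5 |
| All at Week 4 | 9/150 = 6.0% | 1.0 |

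*Persistence varied, no removal:* take steady prevalence p = 2% and probability r that a reaction is still present at the next visit. New onset is q = p(1 − r)/(1 − p), and ever = 1 − (1 − p)(1 − q)^5.
- r = 0: 11.60%, ratio 5.8.
- r = 0.5: 6.90%, ratio 3.45.
- r = 0.8: 3.98%, ratio 1.99.

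*Visits reached varied, constant risk of 1% to 5%:* the ratio is 1.0 for one visit, 1.95 to 1.99 for two, 2.85 to 2.97 for three and 5.30 to 5.85 for six. The number of visits is a general ceiling. The subjects ever affected cannot exceed the sum of the row counts, and each row count is at most the highest percentage times the arm size.

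The value 1.0 is the low end of these scenarios, not a floor. A late row with few subjects left could read higher than the ever-affected share.

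**The case against.** The best reply is that the reactions that matter most are already counted. One that ends treatment appears, per subject and over the whole study, in the AE summaries and among the discontinuations, and AEs have their own severity grading. By-visit tables do not claim to estimate cumulative risk, so no stated figure is wrong. The trial was terminated and the SAP is purely descriptive. All of this stands. It confines the gap to scored reactions not reported as AEs, and to counts on the tolerability scales themselves.

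Two stronger readings are tempting and should not be drawn.
- **That a single severe reaction ends treatment and then shows in one visit row only.** For a Dermal Response Score of 5, Protocol 5.9 provides for interruption first and permanent discontinuation on recurrence. A single event can stop treatment through the SAE or clinically significant AE clause of that section, but it then enters the AE outputs. Nor do the documents show such subjects returning untreated with scores of 0: the interruption lasts up to one week and visits are four weeks apart.
- **That the share affected is understated several-fold.** This needs one-off reactions spread fairly evenly over many visits. The documents give no timing or persistence, and SAP Section 3 says only that no subject finished the treatment period, not how many visits were reached.

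**Conclusion.** The point holds as a gap in reporting. Both documents show the tolerability scales only by visit, among those with data, and nothing planned gives the share of each arm ever reaching a given score. The AE tables cover reactions reported as AEs and do not cover the rest.

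The size cannot be fixed from the documents. Across the assumed patterns the ever-affected share is 1.0 to about 5.9 times the highest visit percentage. Early clustering, persistence and few visits all pull the ratio down. The upper end needs one-off reactions, even spread and all six visits, which no subject in this trial completed on treatment. It is a cheap improvement, not an error that overturns a stated result.

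**What to change.** Keep the by-visit tables and add to SAP 9.2 one table by arm of each subject's worst score:
- **Dermal Response and Other Effects:** worst post-baseline score, from scheduled and Early Termination assessments and any unscheduled ones recorded, among Safety subjects with at least one such assessment. State the ranking used for Other Effects, since G is the code for no effect.
- **Subject burning/stinging:** worst score after any in-clinic application, Day 1 included, among Safety subjects with at least one such score. SAP 6.1.1 labels the Day 1 score as baseline, so a post-baseline rule would discard the first-dose reading.
- **Mistimed baselines:** SAP 9.2 removes such subjects from the summary completely. Do not drop their later scores from the new table.
- **Cross-reference** the subjects who stopped study drug or phototherapy because of an AE, and note that visit rows are not the risk of a reaction.

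The cost is one more table. The data are already collected, except that Protocol 5.6 does not list local tolerability among unscheduled-visit procedures, so those scores can be used only where they exist. The downside is that reported reaction rates will look less favourable than the visit rows.

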#### **6.3.3. Medical History and Physical Examinations**

Clinically significant changes observed during physical examination will be captured as adverse events and included in AE tabulations.

#### **6.3.4. Clinical Laboratory Results and Vital Signs**

All clinical laboratory results and ECG measurements and their change from Baseline (pre dose), will be summarized descriptively by parameter, along with time point of collection.

A shift table describing out-of-normal range shifts will be provided for clinical laboratory results.

### **6.3.5. Prior and Concomitant Medications**

Prior and concomitant medication information for all enrolled/randomized subjects will be presented in electronic datasets. Summary tables will be presented by World Health Organization-Anatomical Therapeutic Chemical Classification System (WHO-ATC) therapeutic category and product.

### **6.3.6. Pharmacokinetic Analysis**

Plasma drug concentrations at pre-dose will be summarized using descriptive statistics.

A manual for blood sampling, collection, processing, and sample shipment will be provided in a separate document.

## **7. STUDY ADMINISTRATION**

### **7.1. Ethics**

#### **7.1.1. Ethics Review Board**

Before enrollment of subjects into the study, the current protocol and ICF will be reviewed and approved by an appropriate IRB or IEC, as required by FDA (21 CFR § 56), Health Canada, ICH GCP regulations and other local/regional regulatory requirements. A letter documenting the IRB or IEC approval must be received by the Sponsor (or delegate) before the initiation of the study at a clinical site. Amendments to the protocol will be subject to the same requirements as the original protocol.

The Investigator, Sponsor, or designee will submit a progress report at least once yearly to the IRB or IEC. However, the frequency of these reports will depend on IRB or IEC requirements. As soon as possible after completion or termination of the study, the Investigator will submit a final report to the IRB or IEC per the IRB or IEC requirements, and in compliance with FDA, Health Canada, local and regional regulations and ICH GCP guidelines.

The Investigator, the Sponsor, or designee shall promptly notify the IRB or IEC of any SAEs, SUSARs, or any other information that may affect the safe use of the investigational products during the study, per the IRB or IEC local requirements, and in compliance with FDA and Health Canada regulations and ICH GCP guidelines.

